5. EFFICACY ANALYSIS

5.1. Primary Efficacy Analysis

Not applicable

5.2. Analysis of Efficacy Endpoints in the LTE Period

Analyses of the LTE efficacy endpoints will compare subjects randomized to PTC857 (early start of PTC857) against those randomized to Placebo (late start of PTC857). The two treatment groups will be labelled as utreloxastat/utreloxastat and Placebo/utreloxastat and will include all available efficacy results from the entire study period (parts A, B and C).

Analyses will be performed for both the ITT1 and ITT2 analyses sets.

5.2.1. Change from Baseline in ALSFRS-R

Change from baseline in ALSFRS-R at Weeks 52 and 160 will be evaluated by means of a mixed model repeated measures analysis using all available ALSFRS-R scores up to Week 160.

The model will include fixed categorical effects of treatment (PTC857 or placebo), use of approved background therapy for ALS at screening (Yes vs No), the amount of change in the subject's ALSFRS-R score during the Screening Period (<1, 1-2 or 3-4 points total loss), time of collection (nominal week at the visit as a categorical variable), as well as the continuous, fixed covariates of baseline ALSFRS-R, and The TRICALS risk profile. In addition, the following interaction terms will be included: Time by treatment, time by baseline ALSFRS-R, and TRICALS risk profile by time. Subject will be included as a random effect. The Restricted Maximum Likelihood (REML) estimation approach will be used with the variance-covariance structure set as unstructured (UN). Other types of covariance matrices will be explored in the case of non-convergence of the UN. Subjects with no post baseline results for the outcome variable will be excluded. This analysis will be performed for both the ITT1 and ITT2 analysis sets.

Observed and change-from-baseline values will also be summarized descriptively at each visit.

In supplementary analyses, score changes from baseline at Weeks 52 and 160 for the ALSFRS-R subdomains will be analyzed under the same estimand framework where MMRM models will be used to implicitly impute missing data. Nominal P-values for the treatment arm comparison, estimate of LSMEANS for the treatment differences (PTC857 – Placebo) at Weeks 52 and 160, and the two-sided 95% confidence intervals of the LSMEANS difference will be presented.

To determine if there is a reduction in the decline of ALSFRS-R scores in subjects randomized to placebo after starting open-label PTC857, graphical plots comparing the decline during the double-blind period and the open-label extension periods will be provided. Additionally, changes (in ALSFRS-R) from both the initial study baseline and the treatment baseline in Part B will be reported.

5.3. Analysis of Continuous Long Term Extension Endpoints

The following continuous long term extension endpoints will be analyzed for both the ITT1 and ITT2 analysis sets using a similar model as described in Section 5.2.1, p-values for the treatment arm comparison, estimate of LSMEANS for the treatment differences (PTC857 – Placebo), and the two-sided 95% confidence intervals of the LSMEANS difference will be presented:

- Quality of life as assessed by Amyotrophic Lateral Sclerosis Assessment Questionnaire (ALSAQ-40) at 52 and 160 weeks.
- Change from baseline in Modified Norris Scale total score at 52 weeks.
- Change from baseline in slow vital capacity (SVC) as assessed by pulmonary function tests (PFTs) at 52 weeks.
- Change from baseline in neuropsychological function as assessed by the ALS CBS at 52 weeks.
- Change from baseline in log transformed NfL (plasma) at 52 weeks. Geometric means and mean ratios to baseline, as well as the difference in geometric mean ratio for those in the PTC875 arm to those in the Placebo arm will be reported, together with 95% confidence intervals and p-values.

5.4. Overall Survival

Overall survival (OS) is defined as the time in months from the date of first dose to the date of death from any cause or date last known alive for those who did not die.

Specifically,

OS = Date of death or date last known alive – Date of first dose + 1

Subjects will be censored at the last date they are known to be alive. The last known alive date will be the last date of any subject record in the study database. The date may be the last visit date or last contact date that the subject is known to be alive. Subjects who only have baseline record will be censored at the first dose date.

OS will be analyzed using KM methods. A summary table of the number of deaths, the number of censors, and KM estimates (25th, 50th, 75th percentile of OS along with the 95% CI). Kaplan-Meier survival curves will also be presented.

A stratified Cox Proportional Hazards regression model will be used to estimate the hazard ratio (and 95% CIs) of PTC857 compared to Placebo. The model will be stratified by the amount of change in the subject's ALSFRS-R score during the Screening Period (<1, 1-2 and 3-4-points total loss), and use of approved background therapy for ALS at screening (Yes vs No). In addition, the TRICALS risk profile and ALSFRS-R score at baseline will be included in the model as covariates. Ties in survival time will be handled using the Breslow method.

Kaplan-Meier survival curves will also be presented.

5.5. Analysis of Exploratory Endpoints in the LTE

Exploratory endpoints will be summarized for both the ITT1 and ITT2 analysis sets. Summary statistics by nominal timepoint will be provided for all the exploratory endpoints, including ALS-CBS, EQ5D-5L, and urine p75 neurotrophin receptor (p75NTR).

ALS-CBS total score will be analyzed using the same methodology described for secondary (continuous) endpoints in Section 5.3. P-values for the treatment arm comparison at week 52, estimate of LSMEANS for the treatment differences (PTC857 – Placebo), and the two-sided 95% confidence intervals of the LSMEANS difference will be presented.

6. SAFETY ANALYSES

Safety will be assessed based on exposure, and will include adverse events, laboratory assessments, vital signs, 12-Lead electrocardiogram, physical examination, and Columbia-Suicide Severity Rating Scale (C-SSRS). The results will be descriptive in nature. All data will be summarized and listed. There will be no statistical comparisons between the treatment groups for safety data, unless otherwise specified within the relevant section. All data will be summarized and listed.

6.1.1. Pooling of Safety Analyses

Safety data will be reported for the pooled open-label long-term extension period (Parts B and C) as well as for the entire pooled study period (Parts A, B, and C).

Safety summaries for the open long-term extension periods, (Parts B and C) will be based on The Long-Term Extension Safety Population (defined in Section 2.4). These summaries will be displayed by actual treatment received during the double-blind treatment period and long-term extension periods. Tabular outputs will have columns labeled as follows:

- Placebo / Utreloxastat (subjects initially randomized to placebo)
- Utreloxastat / Utreloxastat (subjects initially randomized to utreloxastat)
- Total

The safety summaries for the entire pooled study period (Parts A, B, and C) will be presented in a single total column and will be limited to the subset of the Safety Analysis Set consisting of subjects who received the actual investigational product (PTC857).

6.2. Extent of Exposure

The extent of exposure to study drug will be summarized descriptively. The summaries will include mean, SD, median, minimum, and maximum values.

The extent of study drug exposure for the open label long-term extension period is defined as the difference between the last dose of study medication and the first dose study drug in the open label long-term extension period plus 1.

Extent of exposure to PTC857 during the whole study period will also be summarized. Extent of exposure to PTC857 will be defined as the difference in time between first exposure to PTC857 and the last dose of PTC857.

6.3. Adverse Events

6.3.1. Reporting of Adverse Event Data

Adverse events will be collected and recorded from the time subjects sign the informed consent form to the end of the follow-up period. All AEs will be classified by primary system organ class (SOC) and preferred term (PT) according to the MedDRA coding dictionary. A treatment-emergent adverse event (TEAE) is an AE that begins after the first administration of study drug or any existing AEs that worsens after the first dose of study drug. All reported AEs will be listed, but only TEAEs will be summarized in tables.

AEs with an onset from day 1 of the open label long-term extension periods up to and including 30 days after the last dose of study drug in the open label long-term treatment periods (or up to and not including the start date of the Continued LTE period whichever comes first) will be considered as occurring during the LTE treatment period.

An overall summary of TEAEs, including the number and percentage of subjects reporting at least one TEAE for the categories listed below, will be provided.

- Subjects with at least one TEAE
- Subjects with at least one TEAE related to study drug
- Subjects with at least one serious TEAE
- Subjects with at least one non-serious TEAE
- Subjects with at least one serious TEAE related to study drug
- Subjects with at least one TEAE leading to premature discontinuation of study drug
- Subjects with at least one TEAE leading to death
- TEAEs by highest relationship to study drug
- TEAEs by highest severity

The following summaries will be tabulated:

- TEAEs overall and by SOC and PT
- TEAEs occurring in \geq 5% of subjects within a treatment group, by PT
- TEAEs by PT
- Study drug related TEAEs, overall and by SOC and PT
- TEAEs by maximum severity, overall and by SOC and PT
- Grade 3 or Higher TEAEs by SOC and PT
- Grade 3 or higher related TEAE by SOC and PT
- TEAEs by highest relationship to study drug
- Serious TEAEs, overall and by SOC and PT
- Serious TEAEs, overall and by severity grade, SOC and PT
- Non-serious TEAEs, overall and by severity grade, SOC and PT
- TEAEs leading to discontinuation of study drug, overall and by SOC and PT
- TEAEs leading to death, overall and by SOC and PT

TEAEs with "possibly related", "probably related" or "related" to study drug based on the investigator assessment will be considered as drug related TEAEs. TEAEs with missing causality, if any, will be assumed as 'Related AEs'.

For summaries by SOC and PT, a subject will be counted only once at the SOC level and once at each PT within the SOC level, even if the subject experienced more than one AE within a

specific SOC and PT. For summaries by SOC, PT, and maximum severity, a subject will be counted only once at the maximum severity level for which the event occurred at the SOC level and at the maximum severity level for which the event occurred for each unique PT within that SOC level. Therefore, subjects will contribute to only one severity level within a PT or SOC.

Summaries presenting frequency of TEAEs by SOC and PT will be ordered by overall descending frequency of SOC and then, within a SOC, by overall descending frequency of PT. Summaries presenting TEAEs by PT only will be ordered by overall descending frequency of PT.

TEAE summaries for the LTE periods (Parts B and C) will be displayed by actual treatment received during the double-blind period and the long-term extension periods.

TEAE summaries for the entire trial period (Parts A, B and C combined) will be presented with a total column only and will include subjects exposed to actual PTC857.

Subject listings of all adverse events will be provided. Deaths and other serious or clinically significant non-fatal adverse events will be listed separately.

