3.2.6. Study Treatment Periods

Period	Definition
Pre-treatment Period	Date of Screening through one day prior Date of first dose
Double-blind	Date of first dose through one day after Date of last dose

Treatment Period	OR
	Date of first dose through one day prior first dose during open-label treatment
	period
Open label Long-	Date of first dose during open-label LTE period (Part B) to Date of last dose
term Extension	during open-label LTE period (Part B or C) plus one
Periods	OR
	Date of first dose during open-label LTE period (Part B) through one after Date of
	last dose during open-label continued-LTE period (Part C)

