3.4. Changes to Protocol Specified Analysis

Safety data for Parts B and C will be combined, as the transition from Part B to Part C does not represent a clinically significant timepoint.

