6.3.2. Exposure Adjusted incidence rates (EAIR)

Exposure-adjusted incidence rates (EAIRs) of treatment-emergent adverse events (TEAEs) will be presented by treatment group, MedDRA System Organ Class (SOC), and preferred term, as well as by treatment group and MedDRA preferred term.

For each grouping of subjects (e.g., "All subjects" and "subjects on PTC857), the EAIR of a specific treatment-emergent event is defined as the number of subjects experiencing the event at least once, divided by the total exposure-adjusted follow-up time in person-years.

For subjects who experience the event, the exposure-adjusted follow-up time will be calculated from the first exposure (to PTC857 in Part B) until the first occurrence of the event. For subjects who do not experience the event (censored), the follow-up time will be calculated from the first dose during the safety reporting period until their last safety follow-up for that period.

EAIR will also be calculated for the subset of subjects exposed to the IP (PTC857), for those summaries, the start period of exposure will be defined at the date the subject first took PTC857.

Missing or partial AE onset dates will be imputed using the imputation rules described in Appendix 2.

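### The extension SAP's adverse-event window stops where Part C starts although Parts B and C are pooled, and its A+B+C tables for PTC857 do not exclude events that began on placebo

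*SAP*

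**What the plan says.** All sections below are in the SAP for Parts B and C unless stated.

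**Extension window.** Section 6.3.1 starts the adverse-event window on day 1 of the open-label extension periods. It ends 30 days after the last open-label dose, "or up to and not including the start date of the Continued LTE period whichever comes first". Section 3.2.6 instead ends the open-label period at the last dose "during open-label LTE period (Part B or C) plus one". Section 3.4 declares as a change from the protocol that "Safety data for Parts B and C will be combined", on the ground that the move from B to C is not a clinically meaningful boundary. Section 6.1.1 repeats the pooling, and Section 6.3.1 itself later says: "TEAE summaries for the LTE periods (Parts B and C) will be displayed by actual treatment received".

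**Exposure-adjusted rates.** For subjects without the event, Section 6.3.2 says "the follow-up time will be calculated from the first dose during the safety reporting period until their last safety follow-up for that period". It does not say which of the two definitions is the period meant.

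**A+B+C summaries.** Section 6.3.1 says a treatment-emergent event "is an AE that begins after the first administration of study drug", or an existing one that worsens after that dose. It adds: "TEAE summaries for the entire trial period (Parts A, B and C combined) will be presented with a total column only". Sections 6.1.1 and 6.3.1 limit this column to subjects who received PTC857. Neither limits when the event began.

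**The concern.** The two definitions of the extension period cannot both govern a table headed Parts B and C. One programmer following the Section 6.3.1 clause drops every Part C onset. Another following Sections 3.2.6 and 3.4 keeps them. The counts differ, and the plan does not say which is intended.

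The B+C tables are the only extension adverse-event tables split by original treatment, so the single-column A+B+C table cannot replace them. Late onsets are part of what the extension is for. The protocol reports mammary adenocarcinomas in the 6-month rat study (Section 1.4.1), says their clinical relevance is not yet known (Section 1.5.1), and schedules breast imaging through Day 1121 (Table 3).

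The A+B+C column has a different fault. It is meant to describe safety on PTC857, yet a subject randomized to placebo who later crosses over brings 24 weeks of placebo-phase events into it. The exposure-adjusted rates for the same subjects start the clock at first PTC857, so those events fall before time zero.

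**Working it through.** **Timeline, reproduced first.** The alignment table in Section 3.2.2 puts Day 1121 at 136 weeks after Day 169.

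- (1121 − 169)/7 = 136 weeks, which matches.
- Part B: (365 − 169)/7 = 28 weeks. Part C: (1121 − 365)/7 = 108 weeks. 28 + 108 = 136.
- Total participation in Section 1.1: 8 + 24 + 28 + 108 + 4 = 172 weeks, which matches.

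**Share of planned open-label time outside the Section 6.3.1 window.**

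| Subject | Calculation | Share omitted |
|---|---|---|
| Completes Part C | 108/136 | 79% |
| Stops halfway through Part C | 54/(28 + 54) = 54/82 | 66% |
| Never enters Part C | 0/28 | 0% |

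In days, for a completer and with the 30-day tail: the full window is 952 + 30 = 982 days and the window as written is 365 − 169 = 196 days. The omitted share is 786/982 = 80%.

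**Exposure-adjusted rates for B+C.** Take Part C completers, a constant event rate and a rare event. The ratio of the reported rate to the true rate is then:

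- narrow window for events, pooled period for follow-up: 28/136 = 0.21;
- narrow window for both: 28/28 = 1.0;
- pooled period for both: 136/136 = 1.0.

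The understatement arises only if the definitions are mixed.

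**Placebo-phase events in the A+B+C column.** The rules compare as follows.

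| Item | Anchor in the PTC857-exposed summaries | Section |
|---|---|---|
| Prior medications | first PTC857 | 4.5 |
| Extent of exposure | first PTC857 | 6.2 |
| Start of exposure-adjusted follow-up | first PTC857 | 6.3.2 |
| Treatment-emergent event | first study drug | 6.3.1 |

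Study drug includes placebo: Section 5.2.2 of the protocol lists both under that term. Section 6.1.1 also has to take a subset of the Safety Analysis Set to isolate subjects who received PTC857.

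*Time before zero.* Suppose a placebo subject has a first event on Day 29 and first PTC857 on Day 169. Follow-up to the event is 29 − 169 = −140 days.

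*Upper bound on placebo time.* About 340/3 = 113 subjects are planned for placebo. If all enter Part B, 113 × 24 = 2,712 person-weeks, and 2,712 × 7/365.25 = 52 person-years. Against the planned A+B+C time of all 340 subjects:

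- all complete Part C: 2,712/(340 × 160) = 2,712/54,400 = 5.0%;
- all stop after Part B: 2,712/(340 × 52) = 2,712/17,680 = 15.3%.

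The documents give no rate of entry to the extension. If 40% of placebo subjects entered, the figure would be about 21 person-years.

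**The case against.** **The clause may be a leftover.** It has the same form as the clause in Section 6.2 of the Part A SAP, where it suits a stand-alone period. A careful programmer who has read Sections 3.4 and 6.1.1 would probably query it before dropping Part C from a table headed Parts B and C. That is likely, but it confirms that the text needs correcting.

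**It may be a Part B window.** Sections 1.3.1 and 1.3.2 keep separate adverse-event endpoints for Parts B and C, and Section 1.1 still says the parts are reported separately. This reading does not hold. The sentence starts from the extension periods in the plural, no matching Part C window exists, and Section 3.4 names pooling as the change from the protocol.

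**Nothing is lost.** Part C onsets remain in the A+B+C tables and the listings. This is true and limits the harm, but it does not repair the B+C tables by original treatment.

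**The plan never says outright that placebo-phase events count.** This is also true. The result follows from the only treatment-emergence rule given together with a restriction on subjects alone. The intent to work from first PTC857 is visible elsewhere, and routine checks should catch a negative follow-up time.

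**The person-time shares measure neither affected output.** This stands. Incidence tables contain no person-time, and the PTC857-exposed rates already start at first PTC857. A subject also counts once per preferred term, so a placebo-phase event changes a term's count only if that subject does not have the same term after crossover. The shares bound planned placebo time and do not estimate the excess of events.

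**Conclusion.** Both parts hold; the text is wrong as written and should be fixed.

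The Section 6.3.1 window contradicts Sections 3.2.6, 3.4 and 6.1.1 and the later text of Section 6.3.1. Its effect on the B+C incidence tables depends on how far subjects go into Part C, from none to about four-fifths of planned open-label time. These are shares of planned time, not of events. The B+C exposure-adjusted rates are understated only if different periods are used for events and follow-up.

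For the A+B+C summaries, following the stated rules counts placebo-phase events of subjects who later took PTC857 and can produce negative follow-up. At most 52 person-years of placebo time are involved, assuming every placebo subject enters Part B. The number of extra events cannot be derived from the documents.

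All of these results are descriptive, and the Part A primary analysis is not affected.

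**What to change.** - **Section 6.3.1, window:** replace the parenthesis so that pooled B+C events run from the first open-label dose to 30 days after the last open-label dose in Part B or C.
- **Section 6.3.2:** state that this same period defines both the events counted and the follow-up time in the B+C rates.
- **Section 6.3.1, A+B+C summaries of PTC857-exposed subjects:** define a treatment-emergent event as one that begins or worsens on or after the first PTC857 dose, and apply this to the counts and to the numerator of the exposure-adjusted rates.

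If separate Part B and Part C tables are still wanted, each needs its own named window, and Section 1.1 should be reconciled with Section 3.4.

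The cost is two or three sentences in the extension SAP and no new data.

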6.3.2. Exposure Adjusted incidence rates (EAIR)

Exposure-adjusted incidence rates (EAIRs) of treatment-emergent adverse events (TEAEs) will be presented by treatment group, MedDRA System Organ Class (SOC), and preferred term, as well as by treatment group and MedDRA preferred term.

For each grouping of subjects (e.g., "All subjects" and "subjects on PTC857), the EAIR of a specific treatment-emergent event is defined as the number of subjects experiencing the event at least once, divided by the total exposure-adjusted follow-up time in person-years.

For subjects who experience the event, the exposure-adjusted follow-up time will be calculated from the first exposure (to PTC857 in Part B) until the first occurrence of the event. For subjects who do not experience the event (censored), the follow-up time will be calculated from the first dose during the safety reporting period until their last safety follow-up for that period.

EAIR will also be calculated for the subset of subjects exposed to the IP (PTC857), for those summaries, the start period of exposure will be defined at the date the subject first took PTC857.

Missing or partial AE onset dates will be imputed using the imputation rules described in Appendix 2.

6.4. Laboratory Values

All clinical laboratory analyses will be performed by the central laboratory. The clinical laboratory assessment of hematology, clinical chemistry, and urinalysis will be obtained at scheduled visits. The following parameters are collected at the following visits per protocol:

Parameter(s)	Scheduled Visit(s)
Hematology: Hemoglobin, Hematocrit, RBC count,	Screening, Day 1, Day 29, Day 57, Day
Reticulocytes, Platelet count, WBC count, Neutrophils,	85, Day 169, Day 197, Day 225, Day 253,
Eosinophils, Monocytes, Basophils, Lymphocytes, Mean	Day 365, Day 533, Day 701, Day 869,
corpuscular volume	Day 1037, and ET
Clinical Chemistry: Urea, Creatinine, Fasting glucose,	Screening, Day 1, Day 29, Day 57, Day
Sodium, Potassium, ALT, AST, GGT, Bilirubin (total,	85, Day 169, Day 197, Day 225, Day 253,
direct/indirect), Alkaline phosphatase, Albumin,	

Parameter(s)	Scheduled Visit(s)
	Day 365, Day 533, Day 701, Day 869,
	Day 1037, and ET
Lipid Profiles: Cholesterol (total), LDL, HDL, Triglycerides,	Screening, Day 1, Day 14, Day 29, Day
LDH	57, Day 85, Day 169, Day 183, Day 197,
	Day 225, Day 253, Day 365, and ET
Urinalysis: Urobilinogen, Nitrite, pH, Glucose, Total	Screening, Day 1, Day 85, Day 169, , Day
protein, Erythrocytes, Leukocytes, Ketones, Microscopy,	253, Day 365, Day 533, Day 701, Day
Specific gravity, Bilirubin	869, Day 1037 and ET
Coagulation: PT [sec], PT [INR], aPTT	Screening, Day 1, Day 29, Day 57, Day
	85, Day 169, Day 197, Day 225, Day 253,
	Day 365, Day 533, Day 701, Day 869,
	Day 1037, and ET
Pregnancy Test: β-HCG, FSH	Screening, Day 1, Day 29, Day 57, Day
	85, Day113, Day141, Day 169, Day 197,
	Day 225, Day 253, Day 281, Day 309,
	Day 337, Day 365, Days 393, 421, 449,
	477, 505, 533, 561, 589, 617, 645, 673,
	701, 729, 757, 785, 813, 841, 869, 897,
	925, 953, 981, 1009, 1037, 1065, 1093,
	and 1121 and ET

Separate summary tables and listings will be produced for each of the separate groups above (e.g., separate table for hematology and clinical chemistry etc.); however, urinalysis, and serum and urine pregnancy tests will be listed only. The International System of units (SI units) will be used for all summary and data listing displays unless otherwise indicated.

Laboratory data will be summarized descriptively by visit for each laboratory parameter. Both observed results and changes from baseline will be summarized for continuous variables. Laboratory values will be categorized as clinical grade (low/normal/high) according to normal ranges. Shifts from baseline to the last on-treatment value and the worst on-treatment value will be presented. For these shift summaries, for the last on-treatment summary only scheduled visits will be taken; for the worst on-treatment summaries unscheduled assessments will be included in the assessment of worst. Both worst low and worst high will be summarized.

Laboratory values that are below the limit of quantification will be imputed as the lower-limit of quantification, similarly, values above the limit of quantification will be imputed as the upper-limit of quantification for the summary statistics. But for listings, the values will be presented as recorded.

By-subject listings of all the laboratory parameters will be presented that clearly indicate out of normal range values and possible abnormal values for the safety analysis set.

